16.1 Intervention announcement email

16.2 EBPO text

16.3 Participant questionnaire

PRÉCIS

Study Title: Deprescribing to Reduce Injurious Falls among Older Adults with Dementia

Objectives

The overarching objective of this project is to assess the feasibility and acceptability of implementing STOP-FALLS, an evidence-based, deprescribing intervention that targets central nervous system (CNS)-active medications, with older persons with dementia (OPWD) and their care partners, including those from diverse backgrounds. To accomplish this objective, we have the following aims:

Aim 1. Adapt STOP-FALLS for OPWD and their care partner(s). Stakeholder (primary care provider and care partners of OPWD) perspectives will be elicited to inform and guide adaptations. These activities are considered “not human subjects research,” and have been reviewed and determined to be IRB exempt by Kaiser Permanente Washington (KPWA) IRB.

Aim 2. Conduct a one-arm pilot trial of the adapted STOP-FALLS intervention to determine 1) feasibility of reaching OPWD and their care partners, 2) acceptability of the intervention, and 3) whether the intervention was implemented as intended (implementation success).

Aim 3. Establish feasibility of using pragmatic methods to ascertain the following outcomes: 1) medically treated falls (primary outcome), 2) all-cause emergency department visits and hospitalizations (secondary outcome), and 3) nursing home placement (secondary outcome).

Design and Outcomes

The study design for Aims 2 and 3 is a one-arm, health-system embedded pragmatic pilot trial. Outcomes are described above and will be obtained from the virtual data warehouse (VDW) of the health system.

Interventions and Duration

The intervention consists of patient-facing, written brochures on six classes of CNS-active medications and provider decision support in the form of pharmaceutical aids (evidence-based pharmaceutical opinions, or EBPOs). Patient participants will receive a one-time mailing of a brochure, and PCP will receive decision support materials synchronous with the patient participant mailing. Subsequent actions around deprescribing (discussion, tapering) of the medication will be at the discretion of the patient participant and the PCP.

Sample Size and Population

The target sample size is 120 older adults with diagnosed dementia.

STUDY TEAM ROSTER

Principal Investigator:

[name], MS

*University of Washington
Harborview Medical Center
[name]

1. STUDY OBJECTIVES

1.1. Primary Objective

To assess the feasibility and acceptability of implementing STOP-FALLS, an evidence-based, deprescribing intervention that targets central nervous system (CNS)-active medications, with older persons with dementia (OPWD) and their care partners.

1.2. Secondary Objective

To determine the feasibility of using pragmatic methods to ascertain the primary and secondary outcome measures. These outcomes are: 1) medically treated falls (primary outcome), 2) all-cause emergency department visits and hospitalizations, and nursing home placement (secondary outcomes).

2. BACKGROUND AND RATIONALE

2.1. Background on Condition, Disease or Other Primary Study Focus

Falls among older adults are a major public health concern given their multiple adverse consequences including severe injury, functional decline, nursing home placement, and mortality.¹ Older people with dementia (OPWD) have eight to ten times more incident falls compared to age-matched peers without dementia.^{2,3} OPWD are also less likely than those without dementia to make a full functional recovery after a fall-related injury,⁴ and falls increase burden on care partners.^{5,6}

Medications and particularly those that affect the central nervous system (CNS) are a key modifiable risk factor for falls.⁷ Research has found that reducing CNS-active medications can reduce falls.⁸ CNS-active medications are considered potentially inappropriate for older adults, especially for OPWD, and guidelines recommend avoiding their use.⁹ However, use remains common and is increased among OPWD.^{10,11}

2.2. Study Rationale

STOP-FALLS-D seeks to address the guideline-practice gap described under 2.1., above. Our research team adapted a set of best practices^{12,13} for reducing use of CNS-active medications and is currently testing it with older adults *without dementia* in a pragmatic, cluster-randomized trial in primary care clinics of Kaiser Permanente Washington (KPWA). The intervention, called **STOP-FALLS**, (PI: [name], 1 U01CE002967) is a nudge intervention designed to activate patients and providers.¹⁴ It delivers direct-to-patient education and provider decision support about the risks of five classes of CNS-active medications: opioids, sedative-hypnotics, skeletal muscle relaxants, tricyclic antidepressants, and first-generation antihistamines. The intervention is delivered via mail (to patients) and via the electronic medical record (to PCPs). Care partners are not an intervention target, and dementia is one of the exclusion criteria. From the health

equity perspective, given that OPWD are more susceptible to the side effects of CNS-active medications, and also given that they are more likely to be prescribed these medications, it seems reasonable and indeed imperative to attempt to reach them with the proposed intervention.

3. STUDY DESIGN

This study consists of three aims.

The study design for Aim 1 is qualitative, one-on-one interviews with stakeholders. This aim was reviewed and determined to be IRB exempt by KPWA's IRB. The purpose of this aim is to adapt STOP-FALLS intervention materials for older adults living with dementia by conducting interviews with stakeholders (KPWA primary care providers and care partners of OPWD receiving care within KPWA).

The final intervention materials, revised based on the input obtained from stakeholders who participate in Aim 1 interviews, will be submitted in a modification to Advarra to be used for Aims 2 and 3.

Aims 2 and 3 will be reviewed by Advarra. The remainder of the protocol thus pertains to Aims 2 and 3 only.

The study design for Aim 2 is a one-arm, pragmatic, health-system-embedded pilot trial to determine 1) feasibility of reaching OPWD and their care partners, 2) acceptability of the intervention, and 3) whether the intervention was implemented as intended (implementation success).

Aim 3 involves data collection for the pilot trial to establish the feasibility of using pragmatic methods to ascertain the following outcomes: 1) medically treated falls (primary outcome), 2) all-cause emergency department visits and hospitalizations (secondary outcome), and 3) nursing home placement (secondary outcome).

4. SELECTION AND ENROLLMENT OF PARTICIPANTS

4.1. Inclusion Criteria

Participants must meet the following inclusion criteria to participate: 1) KPWA enrollees aged 60 years or older, 2) diagnosed dementia, based on either a dementia diagnosis code or prescription for a cholinesterase inhibitor or memantine, 3) receiving primary care at a KPWA integrated group practice outpatient clinic, and 4) taking at least one

CNS-active medication on a chronic (≥ 3 month) basis, as determined by KPWA prescription fill records. The classes of CNS-active medications targeted by the intervention will be: antipsychotics, opioids, sedative-hypnotics, skeletal muscle relaxants, tricyclic antidepressants, and first-generation antihistamines.

Care partners will be identified as individuals aged 18 years or older who self-identify as a care partner for the person with dementia and return a completed research questionnaire.

4.2. Exclusion Criteria

Participants meeting any of the following criteria will be excluded from study participation: a) residing in a skilled nursing facility; b) cancer diagnosis in the prior 12 months; c) receiving hospice or palliative care; d) legally blind (unable to see print materials).

4.3. Study Enrollment Procedures

1. This project will request a waiver of consent to send out the educational brochure and collect data from the electronic medical record (EMR), because mailed educational material could reasonably be sent to patients from their healthcare home as part of routine care, and because decisions about any changes to medications will rest with the patient, their care partner, and their PCP. Therefore, there will not be a process for the participant to opt-out of the study. See section 11.2 for details. The project will request a waiver of documentation of consent for the questionnaire; completing and returning the questionnaire indicates permission to use responses for research.
2. Before commencing data pulls, the study team will email the Medical Chief at each intervention clinic to alert them that this pilot intervention is going to commence. Because the intervention and implementation are very comparable to that of STOP-FALLS, which these clinicians are already familiar with due to having been based in intervention clinics for the STOP-FALLS trial, a more in-depth clinic presentation to providers is not deemed necessary.
3. Using KPWA automated data under a waiver of HIPAA authorization, the study programmer will identify all potential participants who meet inclusion criteria. The programmer will oversample participants who are of Hispanic ethnicity and whose race is not white. Of this potential participant pool we will identify a total study sample of 120 participants to whom we will mail the study materials.

5. STUDY INTERVENTIONS

5.1. Interventions, Administration and Duration

Aim 2

The study design is a one-arm, pragmatic pilot trial. The intervention will be implemented with up to four clinics and up to 120 OPWD and their care partners. The intervention consists of an educational brochure about a CNS-active medication that the OPWD has been prescribed along with decision support for that individual's PCP. To assess the acceptability of the intervention, a brief questionnaire will be mailed to the OPWD shortly after mailing of the intervention materials. Follow-up for outcomes ascertainment will start at the time of mailing of intervention materials to eligible participants.

1. After the sample has been identified, the study team will send a packet to all eligible participants containing:
 - a. A cover letter addressed to the participant and any care partner they may have. The letter will also contain a study phone number with voicemail to call if either participant or care partner has questions. This voicemail line will be monitored by study staff;
 - b. Educational brochure for the medication class that the participant has been prescribed on a chronic (3 months or longer) basis;
 - c. For most drug classes, a corresponding non-pharmacological self-care sheet, previously approved for STOP FALLS that has been modified based on dementia care partner input (Aim 1 interviews).
2. At the same time, the study team will use the Epic (electronic medical record) "staff message" functionality to send a message letting the PCP know that their patient is included in the study and a link to the EBPO of the relevant medication class. The purpose of this message is to enable the PCP to be prepared to have conversations with participants about their medication use and for these conversations to be guided by the evidence and talking points in the EBPO. The timing of these messages is not aligned with an upcoming clinic visit; it is anticipated that a participant/care partner may initiate the conversation with the provider on their own time schedule.
3. When the participant/care partner receives the mailed packet, they can choose to read the materials or not. Reading all the materials in the packet should take approximately 10 minutes. If they choose, they can discuss the information in the brochure with their PCP.

4. Approximately 1-3 weeks after brochure mailing, the study team will send a brief questionnaire to OPWD and their care partners to ascertain intervention acceptability including the perceived usefulness of the educational materials and the likelihood of starting conversations about their medications with their providers. Care partner sociodemographics will also be obtained via this questionnaire for descriptive purposes. If the participant/care partner choose to complete and return the questionnaire, that activity should take approximately 5 minutes. (see **Supplements/Appendices: Participant questionnaire**)
5. Returned questionnaires will be data-entered, and a survey response dataset will be created.

Aim 3

The automated data pulls and chart review associated with Aim 3 involve data collection for the pilot trial to establish the feasibility of using pragmatic methods to ascertain the following outcomes: 1) medically treated falls (primary outcome), 2) all-cause emergency department visits and hospitalizations (secondary outcome), and 3) nursing home placement (secondary outcome).

Automated data pull

1. The study programmer will modify existing code from STOP-FALLS to pull data from KPWA automated data sources for the following three outcomes:
 - 1) medically treated falls (primary clinical outcome), 2) all-cause emergency department visits and hospitalizations (secondary outcome), and 3) nursing home placement (secondary outcome).
2. An analytic dataset will be created and outcomes data summarized. We anticipate this will take 3-6 months.

Medication taper ascertainment from medical records

1. The study programmer will modify existing code from STOP-FALLS to create flags indicating which participants’ medical records have deprescribing text in the “sig field” (i.e., prescribing instructions) for each CNS-active medication.
2. The KPWA study team members ([name] and [name]) will review up to a 20% random sample of records to adjudicate whether or not the flags correctly identified evidence of a medication taper, completing the following shell table for each record:

Field	Description	Notes:

Study ID	Pre-populated study ID	
ConsumerNo	Pre-populated Consumer Number	PHI
Medication class	Pre-populated med class (e.g. opioid, TCA, benzo)	
Date	Pre-populated date	PHI
Taper flag	Pre-populated (yes/no)	Did the program identify a potential deprescribing plan for the sig field?
KPWA_sig	Pre-populated text	Actual text from sig field
Taper flag correct?	Yes/No/Not sure	Does the adjudicator find information in the medical record to support the "Taper flag"?
Notes:	Text box	Any additional information to support decision making of "taper flag correct" score.

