KPWA electronic data sources	Provider ID, Specialty, Provider Type, primary practice clinic. Data collected so that we can determine who the patients' PCP is for Epic Staff Messaging the EBPO to the correct provider).

Table 2: Data from KPWA to ascertain study outcomes

Source (i.e., from KPWA, or an existing or previous study, etc.)	Key Information/Description of Variables
KPWA electronic data sources	
Diagnosis codes:
 
For outcomes including:
 
 • Injury diagnostic codes • Fall-related diagnostic codes 
For chronic conditions associated with falls, e.g.: arthritis, back pain, knee pain, alcohol use disorder, chronic lung disease, congestive heart failure, diabetes, heart disease, hip fracture, hypertension, obesity, peripheral neuropathy, osteoporosis, Parkinson's disease, stroke, urinary incontinence, impaired vision, impaired hearing, memory problems, non-melanoma cancers, frailty
 
For other diagnoses related to medication prescription for the following conditions: anxiety, depression, insomnia, chronic pain

KPWA electronic data sources	All healthcare utilization for the primary outcome (falls) such as primary care visits, specialty visits, emergency department visits, inpatient stays, nursing home admissions
KPWA electronic data sources	All emergency department visits, inpatient stays, and nursing home admissions
KPWA electronic data sources	
Pharmacy dispensing data (drug name, date of dispensing, strength, quantity, days supply, provider id, NDC) for the following intervention target prescription medication classes: antipsychotics, benzodiazepines, z-drugs, opioids, muscle relaxants, antihistamines, tricyclic antidepressants.
 
In addition, the following medication classes are needed to examine whether target medications were substituted with equally unsafe medications as a result of the intervention: Gabapentinoids, other sedative hypnotics, other antidepressants, NSAIDs.

KPWA electronic data sources	KP's Center for Effectiveness and Safety Research (CESR) Med Order Table information (e.g. instruction for usage, prescription date, medication type)
KPWA electronic data sources	Demographics (e.g., age, sex, race, marital status)

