10.3. Quality Assurance

For Aim 2, to ensure accuracy of the data, we will double input data from the mailed questionnaires. For sig field data, up to 20% of charts will be reviewed to determine if the sig data pulls are accurate.

For Aim 3, the data pulled will be verified as being within the follow-up time window and pertinent to the given study participant by hand-review of the data returned.

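### The implementation-success endpoint has no order-date rule and no baseline check of the sig field, so a taper begun before mailing can count towards the 20%/35% decision

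*Combined protocol and SAP*

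**What the plan says.** **Who enters.** Section 4.1 requires at least one "CNS-active medication on a chronic (≥ 3 month) basis, as determined by KPWA prescription fill records". The exclusions in Section 4.2 are "a) residing in a skilled nursing facility; b) cancer diagnosis in the prior 12 months; c) receiving hospice or palliative care; d) legally blind"; none concerns a taper that is already under way.

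**What is counted.** Section 5.1 (taper ascertainment) has the programmer flag participants whose "medical records have deprescribing text in the" sig field, for each CNS-active drug. The adjudication table carries a "Pre-populated date", but its question is only whether the record supports the flag. Section 6.2 calls implementation successful if at least 35% of participants have a taper plan on record. Section 9.5 makes 35% the green boundary and anything under 20% red.

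**When it is counted.** Section 5.1 starts outcome follow-up at mailing. The schedule in Section 6.1 marks implementation success at 1-3 and 3-6 months and leaves its baseline cell empty.

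**Data and checks.** The source of the sig text, "Med Order Table information (e.g. instruction for usage, prescription date, medication type" and so on, is listed in Section 10.1 among the outcome data (Table 2) and not among the data for identifying participants (Table 1). For the sig field, Section 10.3 says under Aim 2 that "up to 20% of charts will be reviewed to determine if the sig data pulls are accurate". The check that data fall inside the follow-up window is stated for Aim 3.

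**The concern.** The endpoint is meant to show whether the mailing and the message to the PCP lead to a taper plan. A person on a slow taper still fills prescriptions, so can meet the fill rule, be mailed a packet and carry taper text in the record when it is read months later. With a single arm, no comparison group removes such cases.

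Section 9.2 names this endpoint as primary for sample size, and Section 9.5 uses it to decide whether a confirmatory study goes ahead. Every existing taper that is counted pushes the proportion up, so a yellow result could be read as green, or a red one as yellow.

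**Working it through.** **1. Does any passage require the taper to be new?**

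| Place | What it fixes | Taper new since mailing? |
|---|---|---|
| 4.1, 4.2 | fill history, four exclusions | not addressed |
| 5.1, start of follow-up | outcome follow-up begins at mailing | implied window only |
| 5.1, flag and adjudication | taper text present, flag supported | no; a date is held but no rule uses it |
| 6.1 | record assessed at 1-3 and 3-6 months | says when it is read, not which orders count |
| 6.2, 9.5 | share with a taper plan | no |
| 10.3 | accuracy of sig pulls | no |

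A post-mailing window is implied but not written into the endpoint. Even if it were applied strictly, a taper begun earlier can produce a further order with taper text after mailing, and that order would fall inside the window. Only a look at the sig field before mailing separates the two, and none is described.

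**2. The plan's own sample size.** Inputs from Section 9.2: 20% against 35%, one-sided 5% alpha, 90% power.

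- Normal approximation: n₀ = [(1.645·√(0.20·0.80) + 1.282·√(0.35·0.65)) / 0.15]² = 71.6.
- With continuity correction: n = (n₀/4)·[1 + √(1 + 2/(n₀·0.15))]² = 78.1.

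This agrees with the stated 78, which is not in dispute.

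**3. Effect of existing tapers.** Let m be the number of the 120 who were already tapering and are counted as successes. Let p be the rate of new tapers among the other 120 − m. The documents give neither, so both are assumed. Green needs 0.35 × 120 = 42 successes, and not red needs 0.20 × 120 = 24.

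- Expected rate = [m + (120 − m)·p] / 120
- P(green) = P(Bin(120 − m, p) ≥ 42 − m)
- P(not red) = P(Bin(120 − m, p) ≥ 24 − m)

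| p | m | Expected rate | Probability |
|---|---|---|---|
| 30% (yellow) | 0 | 30.0% | green 14% |
| 30% | 2 | 31.2% | green 20% |
| 30% | 6 | 33.5% | green 39% |
| 30% | 12 | 37.0% | green 73% |
| 20% (lower edge of yellow) | 0 | 20.0% | green <0.1% |
| 20% | 12 | 28.0% | green 3% |
| 15% (red) | 0 | 15.0% | not red 8% |
| 15% | 2 | 16.4% | not red 16% |
| 15% | 6 | 19.3% | not red 45% |
| 15% | 12 | 23.5% | not red 90% |

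The share already tapering that would lift the expected rate to 35% is (0.35 − p)/(1 − p). This is 0.05/0.70 = 7.1% at p = 30% and 0.15/0.80 = 18.75% at p = 20%.

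**4. Denominator after the repair.** If 12 people were set aside, 120 − 12 = 108 would remain, still above 78. Green would need 38 (0.35 × 108 = 37.8). At p = 30%, P(Bin(108, 0.30) ≥ 38) is 14%, the same as with no existing tapers.

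**The case against.** The strongest reply is that the plan already places this endpoint after mailing. Outcome follow-up starts then, the baseline cell for implementation success is empty, and Section 10.1 gives the purpose of the chart look as finding out whether deprescribing occurred. Order dates are also held. This stands as far as it goes: a post-mailing window is the natural reading. It does not say which orders count, and it does not deal with an earlier taper whose text recurs.

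A reader might infer more than the documents support:

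- *Existing tapers are scored as successes on day 0.* Nothing is scored at baseline. Such tapers can count later; the text leaves this open.
- *The eligibility screen cannot see a taper.* Table 1 includes strength, quantity, days supply and dispensing date, so a falling dose could be visible. No rule uses it.
- *These people have no untapered drug left for the mailing to act on.* Section 4.1 asks for at least one target drug and the flag works drug by drug, so another target drug may be untapered.
- *Section 10.3 rules out a window check on taper data.* Section 5.1 sets taper ascertainment under Aim 3, while Section 10.3 puts the sig check under Aim 2. The two are ambiguous together.

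The size is also open to challenge. The numbers of existing tapers are assumed, and every one is taken to be flagged. If the implied window is applied, m shrinks to people whose earlier text recurs, which may be one or two. With m = 2 the chance of green at p = 30% moves only from 14% to 20%.

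**Conclusion.** The point holds as a gap in the definition of the endpoint. Nothing requires a counted taper to be new since mailing, and nothing identifies tapers present at baseline. The direction of the bias is upward. Its size cannot be estimated from the documents, and they do not show that any existing taper will in fact be counted.

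Under the assumptions above, the consequence is small when the true new-taper rate is well below a boundary. It can be decisive within about five percentage points of one: at 30%, six existing tapers (5% of the sample) raise the chance of green from 14% to 39%. The stated sample size of 78 is unaffected. This is more than a missing detail, because writing down the implied window would still leave recurring earlier tapers in the numerator. It should be settled before the data pull.

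**What to change.** 1. In Sections 6.2 and 9.5, count success only from sig text in orders dated after that participant's mailing date, and say so in the flag definition in Section 5.1.
2. Run the same flag on the Med Order data over a fixed pre-mailing period, its length stated in advance.
3. Base the green/yellow/red decision on participants and target drugs with no taper text at baseline. Someone with taper text for one drug can stay in for another target drug without it. Report baseline-flagged participants separately.
4. In Section 10.3, state that the follow-up-window check covers the sig data too.

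Eligibility need not change. Excluding people at sampling would rest on a flag whose accuracy the study itself sets out to check, and a rule that matches repeated text across orders goes further than needed.

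The cost is one more run of code that is already being modified, plus wording in the sections named. The price is a slightly smaller denominator, some misclassification where the flag errs at baseline, and probably a less favourable taper rate.

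### The taper adjudication form shows reviewers the program's flag and asks whether the record supports it, so the check is open to agreement bias and its wording is ambiguous when the flag is 'no'

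*Combined protocol and SAP*

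**What the plan says.** Under Medication taper ascertainment from medical records in section 5.1, a program flags deprescribing text in the sig field for each CNS-active medication. Two study team members "will review up to a 20% random sample of records to adjudicate whether or not the flags correctly identified evidence of a medication taper". Section 10.3 describes the same check as quality assurance: "up to 20% of charts will be reviewed to determine if the sig data pulls are accurate".

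A shell table is completed for each sampled record. Three of its fields matter here:

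- **Taper flag.** Pre-populated as yes or no, with the note "Did the program identify a potential deprescribing plan for the sig field".
- **Sig text.** Also pre-populated: "Actual text from sig field".
- **Taper flag correct?** Completed by the adjudicator as "Yes/No/Not sure". The note reads "Does the adjudicator find information in the medical record to support the" flag.

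A free-text notes field follows. The form has no field for the adjudicator's own finding of taper present or absent. Yet section 10.2 says the chart review will record whether deprescribing information is indicated, and its wording.

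Sections 9.2 and 9.5 name implementation success as the primary endpoint. It is red below 20%, yellow from 20% to below 35%, and green from 35%. Section 6.2 measures it by a taper plan documented in the sig field.

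**The concern.** A validation step should compare the program's answer with a judgement formed separately from it. Here the adjudicator sees the answer first and is asked whether the record supports it. Nothing in the plan masks the flag or calls for an independent reading beforehand.

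The second difficulty is what the question means for an unflagged record. The label asks whether the flag is right. The note asks for information supporting the flag, and it is unclear what supporting information for a 'no' would be. A reviewer who finds no taper could defensibly answer 'Yes' (the flag is right) or 'No' (nothing found). Two people do the review, and no rule makes them answer alike.

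At stake is whether the sponsor learns how often the flag misses tapers or finds false ones. That matters for a measure read against fixed cut-offs of 20% and 35%.

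**Working it through.** **The plan's own figure.** The plan gives no figure for the adjudication itself. The endpoint it serves has n=78 (section 9.2), from 20% against 35%, one-sided 5% alpha and 90% power.

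- Normal approximation: n = [(1.645×√(0.20×0.80) + 1.282×√(0.35×0.65)) / 0.15]² = 71.6.
- With continuity correction: (71.6/4)×[1 + √(1 + 2/(71.6×0.15))]² = 78.1.
- The smallest exact binomial sample size is 77.

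The stated 78 is reproduced to within one participant and is not in dispute.

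**What an entry means under each reading of the form.**

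| Flag | Record shows | Label reading: is the flag value right? | Note read as: is there taper information? |
|---|---|---|---|
| Yes | Taper | Yes | Yes |
| Yes | No taper | No | No |
| No | Taper (missed) | No | Yes |
| No | No taper | Yes | No |

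The readings agree for flagged records and are reversed for unflagged ones. The ambiguity therefore falls on the rows that carry the false negatives.

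**How many records are affected.** The sample is random across records, so unflagged ones will be included. Assume one record per participant, the full 20% cap, and 20% to 35% flagged.

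- Records reviewed: 0.20 × 120 = 24.
- Flagged: 24 × 0.20 = 4.8 (about 5) to 24 × 0.35 = 8.4 (about 8).
- Unflagged: 24 − 5 = 19, or 24 − 8 = 16.

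**Effect on the reported agreement.** Suppose the flag is perfectly accurate.

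- Label reading: 24/24.
- Note read as a search for taper information, with 'No' then counted as disagreement: 5/24 (21%) to 8/24 (33%).

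**Why flag error matters at the cut-offs.** Observed rate = sensitivity × true rate + (1 − specificity) × (1 − true rate). With assumed values:

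- True 40%, sensitivity 0.80, specificity 1.00: 0.80 × 0.40 = 32%, yellow instead of green.
- True 30%, sensitivity 1.00, specificity 0.90: 0.30 + 0.10 × 0.70 = 37%, green instead of yellow.

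The two error rates act in opposite directions, so a single overall agreement figure would not be enough.

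**The case against.** The scored field is labelled by whether the flag is correct, and the stated task is to judge the flags' correctness. On that ordinary reading an unflagged record scored 'No' is a missed taper, and misses can be counted because unflagged records are sampled. The row also keeps identifiers, date, sig text and notes, so a doubtful entry can be traced and re-read. The spreadsheet in section 10.2 may hold fields that the shell table does not show. The sig text is in front of the reviewer, which limits how far a wrong flag could mislead. The review covers at most 20% of records, in a one-arm pilot.

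Most of this stands, and it rules out three stronger readings that a reader might infer:

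- **That the check is biased, by a known amount.** The documents show only that it is open to bias. They give no figure from which a size could be derived.
- **That the form cannot be scored consistently, or that false negatives cannot be estimated.** The label permits one coherent reading if both reviewers adopt it. What is missing is anything to ensure that they do.
- **That the endpoint count is wrong.** Nowhere does the plan use the check's result to correct the proportion with a taper plan.

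The objection does not remove the absence of masking, the conflict between label and note for an unflagged record, or the mismatch between the shell table and section 10.2. Tracing entries afterwards also costs more than asking the clearer question at the start.

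**Conclusion.** The point holds as a weakness in the validation step that should be corrected before the review begins. The only accuracy check described for the taper flag shows the adjudicator the flag, does not ask for an independent finding, and is worded ambiguously for unflagged records. Agreement may be overstated, and missed tapers may not be reliably estimated. The form as shown also omits the present/absent finding that section 10.2 says will be recorded.

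The size of any agreement bias is unknown. The 24-record denominator assumes one record per participant. Because flags are made per medication, the number of records could differ. Applying 20% to 35% as the flagged share borrows the participant-level cut-offs. The sensitivity and specificity values are illustrations, as is the range from 24/24 down to 5/24. The harm is to knowledge of how accurate the flag is, not directly to the red, yellow or green result.

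**What to change.** In the shell table of section 5.1:

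1. Hide the 'Taper flag' column from the adjudicator during review.
2. Replace 'Taper flag correct?' with: *Taper plan documented for this medication? Yes / No / Not sure*. Apply it to the plan's existing follow-up window and complete it before the flag is revealed.
3. Have the programmer merge the flag back in, cross-tabulate it against the reviewer's finding, and report agreement separately for flagged and unflagged records, with the 'Not sure' entries shown.

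The sig text may stay visible because it is the source under review, although it can partly hint at the flag, so masking will be incomplete. The new field also brings the form into line with section 10.2. The cost is one reworded column, one hidden column and one merge step, with the same reviewers and the same records.
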